5 STUDY OBJECTIVES

The objective of this Phase 3 study is to evaluate the safety and pharmacokinetics of YKP3089 and concomitant anti epileptic drugs (AEDs) when administered as adjunctive therapy for the treatment of partial seizures.

The evaluations will include:

1. Phenytoin-YKP3089 interaction
2. Phenobarbital-YKP3089 interaction
3. Long term safety of YKP3089 as adjunctive therapy in subjects with partial onset seizures
4. Population pharmacokinetics of YKP3089 and concomitant AEDs

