8 STUDY PROCEDURES AND ASSESSMENTS

The study will include multiple study visits during the 3 years duration. Titration phase will include 7 study visits (Visit 2 to Visit 8), Maintenance phase will include up to 5 visits (Visit 9 to Visit 14). Visit 15 is considered 14-days after last dose follow-up visit. Subjects who benefit from treatment, may continue in an Open-Label Extension beyond year one with visits occurring every 3 months.

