10.3 Visit Windows for Safety Analyses

The table below presents the visits assigned for safety analyses corresponding to the range of treatment study days (window) during which an actual visit (scheduled or unscheduled) may occur. Note that the windows defined for statistical analysis are different from the ones defined in Protocol Section 9.

Visit windows for laboratory tests, vital signs, and for Columbia Suicide Symptoms and Signs Rating Scale (CSSRS):

Derived Visit	Target Study Day [1]	Window [2]
Baseline (for laboratory tests and vitals)	Day 1	Days <= 1
Baseline (for C-SSRS)	Screening (Visit 1)	NA
Visit 2 (for C-SSRS)	Day 1	Days = 1
Visit 3	Day 15	>= Day 2 to <= Day 22
Visit 4	Day 29	>= Day 23 to <= Day 36

Visit 5	Day 43	>= Day 37 to <= Day 50
Visit 6	Day 57	>= Day 51 to <= Day 64
Visit 7	Day 71	>= Day 65 to <= Day 78
Visit 8	Day 85	>= Day 79 to <= Day 92
Visit 9	Day 99	>= Day 93 to <= Day 106
Visit 10	Day 113	>= Day 107 to <= Day 128
Visit 11	Day 143	>= Day 129 to <= Day 173
Visit 12	Day 203	>= Day 174 to <= Day 233
Visit 13	Day 263	>= Day 234 to <= Day 314
Visit 14	Day 365	>= Day 315 to <= Day 410
3 Months after 1 Year Treatment	Day 456	>= Day 411 to <= Day 501
6 Months after 1 Year Treatment	Day 547	>= Day 502 to <= Day 592
9 Months after 1 Year Treatment	Day 638	>= Day 593 to <= Day 684
12 Months after 1 Year Treatment	Day 730	>= Day 685 to <= Day 775
15 Months after 1 Year Treatment	Day 821	>= Day 776 to <= Day 866
18 Months after 1 Year Treatment	Day 912	>= Day 867 to <= Day 957
21 Months after 1 Year Treatment	Day 1003	>= Day 958 to <= Day 1049
24 Months after 1 Year Treatment	Day 1095	>= Day 1050 to <= Day 1112
Visit 15 (14-day follow-up)	Day of the last dose of study	>= day of the last dose of study drug+14

	drug+14 days	
Termination Visit [3]	Termination Visit during treatment period	

[1] Relative to the date of the first dose of study drug. For example, Day 1 = the date of the first dose of study drug.

[2] The study days evaluated for windows of visits during treatment period are on or prior to the last dose day.

[3] For subjects who decide not to continue in the study at any time (i.e., eCRF check box for “Continuing” is answered ‘No’), the Termination Visit is performed (as per Protocol Section 9.1.14). This is available for entry at any time as a separate visit on eCRF. The study day for the termination visit will be assigned relative to the first dose of study drug.

Visit windows for ECG measurements:

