11.4.1 Exposure to YKP3089 study drug

The following will be summarized overall and by safety evaluable subgroups:

- Length of exposure (weeks and months)
- Number and percentages of subjects by time intervals (0-<1 weeks, 1-<2 weeks, 2-<4 weeks, 4 - <12 weeks, 12 - <24 weeks, 24-<48 weeks, 48-<96 weeks, >=96 weeks)
- Number and percentage of subjects by exposure categories: >= 1 dose, >=6 months, >=12 months, >=18 months, >=24 months, >=36 months

For any interim reporting of the results from this study, only applicable exposure categories based on maximum duration of exposure observed will be included in the summary tables).

Derivation for length of exposure to YKP3089:

- Length of exposure to YKP3089 (days) = (stop date – start date + 1).
- Length of exposure to YKP3089 (weeks) = length of exposure to YKP3089 (days)/7
- Length of exposure to YKP3089 (months) = length of exposure to YKP3089 (days)/30.4

Start and stop dates are define as per rules below:

Analysis Period	Subject Participation	
	Enrolled and discontinued study	Enrolled and ongoing at date of data cut-off
Overall	Start Date = First dose date Stop Date = last dose date	Start date = First dose date Stop Date = date of data cut-off
Titration Phase	Start date = First dose date Stop Date = Visit 9 date OR Last dose date	Start date = First dose date Stop Date = Visit 9 date OR date of data cut-off
Maintenance Phase	Start Date = Visit 9 date + 1 Stop Date = Last dose date	Start Date = Visit 9 date + 1 Stop Date = date of data cut-off

Descriptive statistics (mean, standard deviation, median, minimum, and maximum) will be provided to summarize the length of exposure (in weeks and in months) for each safety evaluable subgroup and overall. Similar summary results will be prepared by modal dose within each safety evaluable subgroup.

The number and percentage of subjects at each dose level will be summarized by safety evaluable subgroup and overall for the titration phase, the maintenance phase and overall during study. The length of exposure to YKP3089 at each dose level (from 12.5 mg up to maximum daily dose reported in study) will be summarized using descriptive statistics (mean, standard deviation, median, minimum, and maximum).

Dosing duration will also be expressed in terms of total subject years of exposure to YKP3089, calculated as the sum of all subject exposure days, divided by 365.25.

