13.1 Analysis of Adverse Events (treatment -emergent, non-serious, serious, and deaths)

Adverse events will be coded to a Medical Dictionary for Regulatory Activities Terminology (MedDRA) version 20.0 or later version available at the time of data cut-off. Verbatim description and the MedDRA System Organ Class (SOC) and Preferred Term for all adverse events will be contained in the subject data listings of the clinical study report.

For adverse events with partial start date (i.e., with only month and year are recorded), the following imputation rule will be applied: 15th of the month or fist dose date which one comes later. The imputed date will be used to derive TEAE analysis flag. The actual collected date will be displayed in all AE data listings.

All reported adverse events (regardless of treatment-emergent or not) will be included in a by- subject adverse event listing, with separate by-subjects listings for adverse events and serious adverse events reported for screen failures.

Only treatment-emergent adverse events will be included in summary tables.

Treatment emergent adverse events (TEAE) are defined as AEs with onset after the start of study medication, up to last dose date of study medication + 14 days (or analysis cut-off date whichever comes first), or onset before study medication and worsened after starting study medication, up to last dose date of study medication + 14 days (or analysis cut-off date whichever comes first).

An adverse event is regarded as related to study medication if the relationship to study medication is definite, probable, or possible. Adverse events with missing

relationship will be assumed to be treatment related. Adverse events with missing severity will be assumed to be severe in order to perform the most conservative statistical analysis.

Severe adverse events and adverse events related to treatment will be summarized overall and by safety evaluable subgroups.

TEAE Incidence will be computed as number of subjects with AE/ number of subjects in each reporting group (%).

Incidence of TEAEs leading to study drug discontinuation will report only TEAEs with Action Taken = study drug discontinuation.

In TEAE summary tables, system organ classes (SOCs) will be presented in alphabetical order and preferred terms within each SOC will be presented in descending order of frequency in overall YKP3089 group within each SOC, unless specified otherwise.

The planned summary of adverse events tables are listed below:

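### Adverse events are tabulated only as crude percentages over unequal follow-up; no planned AE table shows incidence by time on drug or uses the subject-years already derived

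*SAP*

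**What the plan says.** One of the four evaluations in SAP section 5 is "Long term safety of YKP3089 as adjunctive therapy in subjects with partial onset seizures". For adverse events, SAP 13.1 defines a single measure: "TEAE Incidence will be computed as number of subjects with AE/ number of subjects in each reporting group". Seven TEAE tables follow. They are arranged by system organ class and preferred term, overall frequency, severity, relatedness, seriousness or drug discontinuation. None is arranged by phase, by time since first dose or by person-time. Protocol 12.4 likewise asks only for number and percent.

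The period over which a subject can contribute an event differs between subjects:
- The TEAE window runs "up to last dose date of study medication + 14 days (or analysis cut-off date whichever comes first").
- SAP 11.4.1 expects a wide spread of exposure: "Number and percentage of subjects by exposure categories: >= 1 dose, >=6 months, >=12 months, >=18 months, >=24 months, >=36 months".
- The last on-treatment visit window in SAP 10.3 is ">= Day 1050 to <= Day 1112", and SAP section 8 says "The study will include multiple study visits during the 3 years duration".
- For ongoing subjects the exposure rule is "Stop Date = date of data cut-off". SAP section 14 allows an early cut-off for regulatory safety reporting and fixes no date.

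The ingredients for a time-based summary are already there. SAP 11.4.1 states "Dosing duration will also be expressed in terms of total subject years of exposure to YKP3089" and defines separate titration and maintenance exposure periods. SAP 8.2.1 defines an onset day for each AE. No planned AE table draws on any of these.

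**The concern.** A crude percentage mixes two things: how often the event occurs, and how long subjects were watched. When follow-up is open-ended and the cut-off can move, the same underlying risk gives a larger percentage in a later report. A reader who sets an early report beside the final one could take longer follow-up for rising risk. The same would happen between the phenytoin, phenobarbital and other-AED subgroups if their follow-up differed; the documents do not say whether it will.

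The second loss is timing. Protocol 4.5.1 builds the study's risk plan around hypersensitivity early in treatment, with a low starting dose, slow titration and visits every two weeks for the first four months. A long-term safety study should be able to show whether events cluster in that period, persist, or first appear later. A table pooled over all follow-up cannot show this.

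**Working it through.** The study is descriptive, with no formal sample size (SAP 9.1, 10.1). The documents give no AE rate, power or event count, so there is no figure of the plan's own to reproduce. The check has three steps.

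**1. Range of follow-up.** SAP 11.4.1 uses 30.4 days per month, so 36 months = 36 × 30.4 = 1,094.4 days. The last on-treatment window ends at Day 1112, and 1112 / 30.4 = 36.6 months. TEAE percentages can therefore pool subjects with one dose and subjects with about three years.

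**2. Events that accrue steadily.** Assumptions, none from the documents: event rate λ = 0.10 per subject-year, entry uniform over 12 months, and 20% annual dropout, so δ = −ln(0.8) = 0.2231 per year. For a cut-off T years after first entry, potential follow-up u is uniform on (T − 1, T), and

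crude incidence = [λ / (λ + δ)] × (1 − m), where m is the mean of exp(−(λ + δ)u) over u.

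Here λ + δ = 0.3231 and λ / (λ + δ) = 0.3095.

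| Cut-off | m | Crude incidence |
|---|---|---|
| 12 months | 0.8545 | 0.3095 × 0.1455 = 4.50% |
| 18 months | 0.7270 | 0.3095 × 0.2730 = 8.45% |
| 24 months | 0.6186 | 0.3095 × 0.3814 = 11.80% |
| 36 months | 0.4478 | 0.3095 × 0.5522 = 17.09% |

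The ratio from 12 to 36 months is 17.09 / 4.50 = 3.8, with the risk unchanged. A simulation of 400,000 subjects per scenario agrees to within 0.1 percentage point, and its first-event rate stays at about 10 per 100 subject-years at every cut-off. Sensitivity at 36 months: with 10% dropout, 0.4869 × (1 − 0.5995) = 19.5%; with 30% dropout, 0.2190 × (1 − 0.3221) = 14.85%.

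**3. Events confined to one period.** Same entry pattern and 20% dropout.
- *Early:* a 5% risk in the first four months, then none. The rate in that period is −3 ln(0.95) = 0.1539 per year. For a subject with at least four months of potential follow-up, crude incidence is [0.1539 / (0.1539 + 0.2231)] × (1 − exp(−0.3770/3)) = 0.4081 × 0.1181 = 4.8%. This applies to everyone at the 18-, 24- and 36-month cut-offs, so the crude figure is stable there (simulated 4.0% at 12 months). The simulated overall rate, by contrast, falls from 8.9 to 5.6, 3.9 and 2.6 per 100 subject-years across the four cut-offs, because event-free later time is added to the denominator.
- *Late:* no risk before month 12, then 10 per 100 subject-years. Simulated crude incidence is 0, 1.0, 3.6 and 9.5%.

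The three patterns differ in kind, yet each report would show a single pooled percentage. Neither that percentage nor one overall rate identifies which pattern holds.

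**The case against.** The case for leaving the plan alone has several good parts.

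- A reader might infer that long-term safety as a whole is reported only as crude percentages. It is not. Laboratory, ECG, vital-sign, physical-examination and C-SSRS results are summarised by visit or timepoint (SAP 13.2 to 13.6), and the windows for laboratory tests, vital signs and C-SSRS extend to Day 1112. The gap is confined to adverse events.
- A reader might infer that interim cut-offs are firmly planned. SAP section 14 only permits one, and requires its date to be noted in the outputs. Numbers ongoing and exposure categories would accompany it (SAP 11.1, 11.4.1).
- A reader might infer that timing is lost altogether. All AEs are listed, and the listings of deaths, other SAEs and AEs leading to discontinuation give days on study. With reported subject-years, a rough rate could be built by hand. What is missing is a planned summary, not the data.
- It is tempting to quote a fivefold distortion: 1 − exp(−0.10t) gives 4.9% at six months and 25.9% at three years. That compares everyone followed for exactly six months with everyone followed for exactly three years, at an assumed constant rate. With staggered entry and dropout the illustration gives about 3.8-fold between 12 and 36 months, and almost no drift for early events after 18 months.
- The study has a single arm and plans no inference, so no treatment comparison is biased.

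These points limit the scope and size of the concern but do not remove it. Interval incidence is itself descriptive, so the absence of inference is no reason to omit it. By-subject listings do not replace a table when the target is at least 1,000 subjects exposed for six months.

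**Conclusion.** The point holds for adverse events. All seven planned TEAE tables are crude percentages over follow-up that may range from one dose to about three years, and none shows when events occurred. For events that accrue over time, the percentage depends on the cut-off: about 4.5% against 17.1% in the illustration, with 14.85% to 19.5% at 36 months for 30% to 10% annual dropout. Those sizes rest on an assumed constant rate, an assumed entry pattern and assumed dropout; none is an estimate for this trial. For events limited to early treatment the percentage is nearly stable, and the loss is only that the table cannot show they were early.

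A reader might also infer that one overall exposure-adjusted rate would cure the problem. It would not: in the early-event illustration that rate falls from 8.9 to 2.6 per 100 subject-years, which could make an early hypersensitivity risk look smaller as follow-up lengthens. The remedy has to be organised by time on drug.

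**What to change.** Keep the crude percentages.

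**Main change.** Add to SAP 13.1 incidence by onset interval for TEAEs, serious TEAEs and TEAEs leading to discontinuation, overall and by subgroup. Suitable intervals would be Weeks 1-12, 13-24, 25-52 and beyond 52. The denominator is the number of subjects still in the treatment-emergent period, and without an earlier occurrence of that event, at the start of the interval. Use fixed day boundaries from first dose rather than phase labels: SAP 11.4.1 ends titration exposure at Visit 9 (target Day 99), which is later than the 12-week titration period.

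**Secondary addition.** Report first events per 100 subject-years at risk, preferably within interval or phase. This matters most for the open-ended last interval, where follow-up is again unequal. The dosing subject-years of SAP 11.4.1 need adapting: time at risk should stop at the first event and otherwise run to the end of the treatment-emergent window. If an overall rate is shown, add a note that it dilutes early risk as follow-up grows. Rates will be imprecise if the phenytoin and phenobarbital subgroups are near their minimum of 20 subjects each.

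**Cost.** A cheap improvement: one more table set and some extra columns from data already collected, with no change to visits or procedures. The downsides are the added output and the care needed in reading overall rates.

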13.2 Analysis of Clinical Laboratory parameters

Individual laboratory values (hematology, chemistry, and urinalysis) will be listed by subject and summarized using descriptive statistics (mean, standard deviation, median, minimum, and maximum) by safety evaluable subgroups and by visit. Both SI and Conventional units will be used in reporting summary results.

Baseline measurement is defined as the last available measurement prior to dosing.

Post-baseline timepoints will be derived as per rules included in [Section 10.3](#).

Individual change from baseline (the last available measurement prior to dosing) in laboratory values will be calculated and summarized descriptively (mean, standard deviation, median, minimum and maximum) for each post-baseline visit. Summary results will be presented by post-baseline timepoints.

Shift tables from baseline to each post-baseline timepoint will be prepared for all laboratory assessments based on the categories of Low, Normal, and High (for numerical results) or Abnormal and Normal (for categorical results).

Overall summary tables for shift from normal/abnormal (low or high) baseline to normal or abnormal post-baseline accounting for all post-baseline results during study will also be prepared. For these summary tables both scheduled and unscheduled post-baseline visits will be considered and subjects will be counted as shift to post-baseline normal if they do not have any abnormal (High or Low) post-baseline results during the treatment period; and as shift to post-baseline abnormal they have at least one post-baseline abnormal (High or Low) post-baseline results.

The following abnormality categories will be derived to evaluate liver function test results:

- AST
 - $\geq 3 \times \text{ULN}$
 - $> 5 \times \text{ULN}$
 - $> 10 \times \text{ULN}$
- ALT
 - $\geq 3 \times \text{ULN}$
 - $> 5 \times \text{ULN}$
 - $> 10 \times \text{ULN}$
- Total Bilirubin
 - $> 1 \times \text{ULN}$
 - $> 1.5 \times \text{ULN}$
 - $\geq 2 \times \text{ULN}$
- Alkaline phosphatase
 - $> 2 \times \text{ULN}$
 - $> 3 \times \text{ULN}$

The number and percentage of subjects with clinical laboratory test values in each category for the laboratory tests listed above will be summarized by each timepoint (including baseline) and overall (ie, anytime post-baseline), and by safety evaluable subgroups.

Pregnancy test results will be listed by subject (females only) by visit.

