1. PROTOCOL SYNOPSIS Design and methodology	
The study will consist of a screening period, open-label titration phase, open label maintenance phase and a taper and follow up.
 
Screening period
 
The screening period for subjects on stable doses of phenytoin or stable doses of phenobarbital or stable doses of other concomitant AEDs will be up to 21 days.
 
Titration phase
 
Subjects on phenytoin or phenobarbital:
 
The titration phase for subjects on stable doses of phenytoin or stable doses of phenobarbital will be 8 weeks. Increasing doses of YKP3089 will be administered (50, 100, 150 and 200mg/day) at 2-week intervals. Sparse sampling of phenytoin, phenobarbital and YKP3089 plasma levels will be
	
The study will consist of a screening period, a 12 week open-label titration phase, an open label maintenance phase and a taper and follow up. Clinic visits during the first 16 weeks of therapy will be every two weeks with a telephone contact between each visit. At each visit during the first 16 weeks physical exams to evaluate signs of hypersensitivity will be performed and laboratory evaluations will be obtained.
 
Screening period
 
The screening period for subjects on stable doses of phenytoin or stable doses of phenobarbital or stable doses of other concomitant AEDs will be up to 21 days.
 
Titration phase
 
Subjects on phenytoin or phenobarbital:
 
The titration phase for subjects on stable doses of phenytoin or stable doses of phenobarbital will be 12 weeks. Increasing doses of YKP3089 will be administered (12.5, 25, 50, 100, 150 and 200mg/day) at 2-week intervals. Sparse sampling of phenytoin, phenobarbital and YKP3089
	
To reduce the rate of DRESS incidence by lowering initial dose of YKP3089 and slowing the rate of titration

Amendment 3

Reasons for Amendment

1. To allow subjects to increase the target dose up to 400 mg/day
2. Minor administrative changes

Amendment 3 Summary of Changes

Section	Old Text	Amended Text	Rationale

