2 LIST OF ABBREVIATIONS

AE	Adverse event
AED	Antiepileptic drug
ALT	Alanine aminotransferase
AST	Aspartate aminotransferase
AUC	Area under the plasma concentration versus time curve
β -hCG	β -human chorionic gonadotropin
CBZ	Carbamazepine
CFR	Code of Federal Regulations
CNS	Central nervous system
C-SSRS	Columbia Suicide Severity Rating Scale
CT	Computed tomography
CYP	Cytochrome P450
DRESS	Drug reaction (or rash) with eosinophilia and systemic symptoms
EC	Ethics committee
ECG	Electrocardiogram
eCRF	Electronic case report form
EEG	Electroencephalograph
FDA	Food and Drug Administration
GABA	Gamma-aminobutyric acid
GCP	Good Clinical Practice
ICH	International Conference on Harmonisation
IND	Investigational new drug
IRB	Institutional review board
IWRS	Interactive Web response system
kg	Kilogram
mg	Milligram
MRI	Magnetic resonance imaging
PHI	Protected health information
PI	Principal Investigator
SAE	Serious adverse event
SKLSI	SK Life Science, Inc.
SUDEP	Sudden unexpected death in epilepsy
SUSAR	Suspected unexpected serious adverse reaction
VNS	Vagal nerve stimulator
VPA	Valproic acid (divalproex sodium)

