After initiating treatment with YKP3089 for two weeks at 12.5 mg and then for two weeks at 25mg YKP3089, subjects taking phenytoin or phenobarbital will titrate YKP3089 upward at a rate of 50mg every other week to a target dose of 200mg/day. This titration is appropriate for this portion of the study because of the known interactions between YKP3089 200mg and phenytoin and phenobarbital. Titrating by 50mg of YKP3089 every other week to steady state will allow better understanding of the clinical impact of any interaction and allow for dosage adjustment of phenytoin or phenobarbital.

Subjects taking concomitant AEDs other than phenytoin or phenobarbital will titrate YKP3089 upward at the same rate to a target dose of 200mg/day.

After reaching a target dose of 200mg, all subjects will be allowed to titrate up to a maximum dose of 400mg/day of YKP3089. A maximum dose of 400mg/day is justified by the additional efficacy seen in the subjects randomized to 400mg/day in the completed dose response study. Seizure free rate effect size in this group approached 20% during the maintenance phase.

4.6 **Potential Risks and Benefits**

Cumulatively, 953 subjects have been exposed to YKP3089 in a total of 14 Phase 1 and 3 Phase 2 clinical studies.

The potential risks in this study includes,

1. Phenytoin dose related toxicity
2. Risk of phenytoin hypersensitivity syndrome
3. Phenobarbital dose related toxicity
4. Rash / hypersensitivity related to YKP3089 exposure
5. DRESS syndrome related to YKP3089 exposure
6. YKP3089 dose related toxicities

Uncontrolled partial epilepsy is a life threatening disease with significant morbidity and elevated standard mortality rates.

The early signs and symptoms associated with hypersensitivity reaction that may progress to DRESS are readily identifiable by patients and clinicians. When detected and adequately managed, progression to DRESS can be prevented or reversed. The potential benefits of YKP3089 include significant partial seizure frequency reduction and substantial seizure free rates (~18%) in patients who continue to suffer seizures despite history of treatment with multiple AEDs. The current benefit/risk profile in conjunction with the risk minimization measures support the enrollment of partial epilepsy patients into this open-label study to assess the profile of YKP3089 as a potential antiepileptic drug

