8.2.2 Other Safety Measures

Concomitant medications and concomitant procedures will be recorded on the Prior and Concomitant eCRF and Concomitant Procedures eCRF, respectively.

Concomitant AED administration since last visit will be recorded on the eCRF page.

Vital signs will be recorded on the Vital Signs eCRF. These data will include blood pressure, heart rate (supine for 5 minutes), temperature, respiratory rate, and weight.

Physical examinations will be recorded on the Physical Exam eCRF. These data will include Body System, normal/abnormal indication, and a description of the abnormality.

Routine 12-lead ECGs will be performed periodically during the study. Parameters including Heart rate, PR interval, QRS interval, RR interval, QT interval, and QTcF will be measured. These results will be recorded on the eCRF.

A brief neurologic evaluation examination will be made and recorded on the eCRF.

Clinical laboratory evaluations will be collected and returned electronically and not entered on an eCRF. Clinical Laboratory Evaluations will include the following:

- Hematology: hemoglobin, hematocrit, white blood count with differential, RBC count, platelet count, and calculated indices.
- Serum chemistry: blood urea nitrogen (BUN), calcium, chloride, creatinine, glucose, total bilirubin, direct bilirubin, alkaline phosphatase, aspartate transaminase (AST), alanine aminotransferase (ALT), total protein, albumin, globulin, sodium, potassium, phosphorus, and glucose. Serum creatinine will be used to calculate the creatinine clearance.
- Urinalysis: pH, specific gravity, protein, glucose, ketone, bilirubin, blood, nitrite, urobilinogen, and microscopic examination
- Pregnancy Tests – All females of child-bearing potential will undergo a serum pregnancy test for β -hCG (β -human chorionic gonadotropin).

All safety laboratory samples will be analyzed by a central laboratory.

The follow-up version of the Columbia Suicide Rating Scale (C-SSRS) will be assessed at Visit 2 and all subsequent visits throughout the study and entered on the eCRF.

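### SAP 13.2 lists eosinophil values and shows their maxima and shifts, but sets no eosinophil threshold and plans no count of subjects with marked eosinophilia, alone or with raised AST/ALT

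*SAP*

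**What the plan says.** Protocol 4.6 lists "DRESS syndrome related to YKP3089 exposure" among the potential risks, and the abbreviation list expands DRESS as "Drug reaction (or rash) with eosinophilia and systemic symptoms". Protocol 4.5.1 reports three cases among 953 exposed subjects and gives early detection of suspected hypersensitivity as the reason for visits every two weeks in the first four months. The amended synopsis text under Amendment 2 adds: "At each visit during the first 16 weeks physical exams to evaluate signs of hypersensitivity will be performed and laboratory evaluations will be obtained".

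The flow chart in SAP Appendix 1 shows safety laboratory draws at each of Visits 3 to 10. SAP 8.2.2 puts "white blood count with differential" in the hematology panel.

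SAP 13.2 plans the following for hematology:

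- a by-subject listing of individual values;
- mean, SD, median, minimum and maximum by visit, for the value and for its change from baseline;
- by-visit shifts: "Shift tables from baseline to each post-baseline timepoint will be prepared for all laboratory assessments based on the categories of Low, Normal, and High";
- an any-time shift between normal and abnormal that uses scheduled and unscheduled results and treats High and Low alike as abnormal.

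It then says "The following abnormality categories will be derived to evaluate liver function test results" and gives multiples of ULN for AST, ALT, total bilirubin and alkaline phosphatase. Subjects in each category are counted at baseline, by timepoint and any time post-baseline. No hematology parameter has such categories.

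**The concern.** Eosinophilia is part of the definition of DRESS, and the draw schedule gives eight early chances to see it. The SAP counts subjects past a stated size of abnormality for liver tests (13.2), QTcF and heart rate (13.3), and blood pressure, pulse, weight, respiration and temperature (13.4). It does not do so for eosinophils. A value just above the upper limit and one several times that limit share the same High cell. None of the seven adverse event tables in SAP 13.1 groups rash, hypersensitivity and DRESS terms.

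At stake is whether the report can state how many subjects had a marked eosinophil rise, and how many had one together with raised transaminases. That number is useful where a reaction was partial, or was not coded as DRESS.

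**Working it through.** The study is descriptive and has no sample-size or power figure to reproduce. The check sets the SAP's rules against each other and then illustrates how little a High flag separates.

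**1. What each planned output can show about a marked rise**

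- *By-visit maximum:* shows the largest value in the window. It does not show how many subjects had a large one.
- *By-visit shift:* counts High without grading it.
- *Any-time shift:* merges High with Low. How much this blurs eosinophils depends on the laboratory's lower limit, which the documents do not give.
- *Listing:* holds every value, with no rule for finding or counting the pattern.

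**2. Which values reach the by-visit tables**

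- Under SAP 10.3, when several results fall in one window, the one nearest the target day is analysed, not the worst.
- On-treatment windows stop at the last dose day, and the Visit 15 window opens at last dose + 14 days. Results from days 1 to 13 after the last dose therefore fall in no window. The exception is a result recorded at the Termination Visit, which SAP 10.3 tabulates under that label.
- Protocol 9.3 has study drug stopped at once when the cause of a rash cannot be definitely determined. A peak drawn at an unscheduled visit after stopping can therefore miss every by-visit maximum and shift.
- The any-time shift is described in SAP 13.2 both as covering the study and as covering the treatment period. It is unclear whether it takes in post-dose results.

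**3. Illustration of size**

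Inputs from the documents: 3 DRESS cases in 953 subjects (Protocol 4.5.1); a target of 1,000 subjects exposed for 6 months (SAP 9.1); draws on Days 15, 29, 43, 57, 71, 85, 99 and 113, which is 8 draws each 14 days apart.

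Program rate: 3/953 = 0.31%, Clopper-Pearson 95% CI 0.06% to 0.92%. Per 1,000 subjects this is 3.15 (0.6 to 9).

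Assumption, not in the documents: a share p of unaffected subjects exceeds the eosinophil upper limit at any one draw. The number High at least once in 8 draws lies between 1,000p (fully correlated draws) and 1,000 x [1 - (1 - p)^8] (independent draws). The last column is 3.15/(3.15 + that number), supposing every DRESS case is itself High.

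| p | High at least once, per 1,000 | DRESS share of High subjects |
|---|---|---|
| 1% | 10 to 77 | 24% to 4% |
| 2.5% | 25 to 183 | 11% to 2% |
| 5% | 50 to 337 | 6% to 1% |

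No planned table reports High at any time. The by-visit shift would carry about 10 to 50 unaffected High subjects per 1,000 at each visit. The any-time table would add Low values and later draws. At the fully correlated end, many of these subjects would already be High at baseline, and the shift layout sets those apart.

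**The case against.** The strongest reply is that the SAP already offers several ways to see a large rise, and this is correct. A reader might infer that eosinophilia appears only as visit means and an ungraded shift, so that DRESS-type rises cannot be seen. The documents do not support that. A large value that enters a window would stand out in the by-visit maximum and in the maximum change from baseline, and it would be in the listing in any case. A calculation showing that three cases barely move the mean tests the wrong statistic.

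A reader might also infer that unrecognised cases stay hidden. Protocol 10.1 makes a laboratory abnormality an adverse event if repeat testing does not refute it, if it suggests organ toxicity, or if it needs active management. Such events enter the adverse event tables by preferred term. Suspected hypersensitivity also calls for an immediate visit.

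Nor do the documents say that the differential was added because of DRESS. The printed rationale for that Amendment 2 row is "To reduce the rate of DRESS incidence by lowering initial dose of YKP3089 and slowing the rate of titration", which names dose and titration. What the text supports is a link between the two-weekly monitoring and the detection of hypersensitivity.

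The rate of 3/953 comes from faster regimens. Protocol Table 5 shows no DRESS in 120 subjects titrated every two weeks, and this trial starts lower still. Zero in 120 does not establish a lower rate, since its upper 97.5% limit is 1 - 0.025^(1/120) = 3.0%, but 3 per 1,000 cannot be taken as a forecast.

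Finally, table templates are separate documents and part of the Protocol 9.3 assessment list is not in the text reviewed, so an eosinophil display elsewhere cannot be excluded. All of this stands. What remains is that the SAP is the place where derived categories are defined, and it defines none for eosinophils.

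**Conclusion.** The point holds as a gap in counting. Large eosinophil rises will usually be visible, at least in the listings, but no planned summary says how many subjects had one, or how many had one with raised AST or ALT. The nearest-to-target rule and the 13 uncovered days after the last dose widen the gap around the time a reaction is most likely to be investigated.

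The size is illustrative: 10 to 337 High subjects per 1,000 over eight draws if p is 1% to 5%, against about 3 DRESS cases per 1,000 (0.6 to 9) at the earlier program rate. The conclusion that a High flag does not isolate marked rises does not depend on the exact p. The figures do depend on it, and on a program rate that may not carry over to the slower titration. This is a low-cost improvement to reporting and not a flaw in how subjects are monitored.

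**What to change.** In SAP 13.2:

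- Add absolute eosinophil count categories in the same form as the liver rows, with cut-offs fixed by the sponsor before database lock.
- Report subjects in each category at baseline, by visit, and any time post-baseline. The any-time row should use the worst value and state that it includes unscheduled results and results after the last dose up to the follow-up visit.
- Add one row counting subjects who meet an eosinophil category and have AST or ALT >=3xULN (the SAP's own lowest transaminase category), with the permitted interval between the two results fixed in advance.
- List those subjects with any adverse event of rash, fever or lymphadenopathy.
- State whether the existing any-time shift covers the whole study or only the treatment period.

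The cost is SAP wording and one or two descriptive tables from central-laboratory data already collected. SAP section 4 allows revision before lock. The downside is that some non-specific eosinophilia will be counted, which the baseline column and the combined row help to put in context. This changes reporting only and alters no clinical rule.
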